1.3.1. Rationale for the Outcome Measures

While no single sperm parameter can predict fertility potential, sperm concentration may be considered the most reliably quantifiable parameter that has potential utility in providing information about male fertility {[U. S. Department of Health and Human Services \(DHHS\) 2018](#)}. Sperm concentration may also be considered the most important parameter of testicular dysfunction {[Sikka 2016](#)}. The present study will evaluate the reduction in sperm concentration of $\geq 50\%$ or more from baseline at 13 weeks as the primary endpoint in accordance with the FDA draft guidance. Significant variations in sperm parameters are expected in men; a threshold of a $\geq 50\%$ reduction, is considered the appropriate threshold to account for normal variability and is consistent with prior studies evaluating impact of potential testicular toxins {[Hellstrom 2008](#), [Hellstrom 2003](#), [Jarvi 2008](#), [Sikka 2014](#)}. Substantial intra- and inter- subject variation can occur particularly in sperm count in patients with and without fertility issues; in one cohort, sperm counts ranged over an order of magnitude in a single healthy patient over time {[Keel 2006](#)}. Two semen samples will be collected for evaluation at each time point during this study, with controlled abstinence periods before each sample collection; longer or shorter abstinence periods may have an impact on quality of sample. Ejaculate volume and sperm number are markedly reduced during periods of high ejaculation frequency {[Oldereid 1984](#)}. Significant variability is noted even in healthy subjects {[World Health Organization \(WHO\) 1999](#), [World Health Organization \(WHO\) 2010](#)}. Additional sperm parameters at 13 weeks will be evaluated as secondary endpoints in alignment with the FDA guidance.

The primary endpoint at Week 13 will enable a direct assessment versus placebo in subjects with moderately to severely active UC or CD. Endpoints at 26 weeks of therapy have been chosen for secondary analyses to assess impact after 2 full spermatogenesis cycles in accordance with draft guidance, which recommends treatment for 26 weeks for drugs that are chronically dosed. The 26-week endpoint will also allow assessment of the impact of longer-term therapy on semen parameters, given the expectation for chronic dosing of therapy in the real world setting. Finally, in the present study, total motility, which is considered to be more consistently measured across observers, will remain as a secondary endpoint.

In this study the Mayo Clinic Score (MCS) will be utilized to define moderately to severely active UC for the purpose of eligibility. The minimum MCS of 6 (including endoscopic and physician global assessment scores of 2 or 3) ensures that subjects will have endoscopic evidence of disease (ie, active disease), have active symptoms (eg, blood in the stool or increased stool

frequency), and be determined by the provider to have moderately to severely active UC. After randomization, the partial MCS will be utilized to determine Responder, Non-responder, and Disease Worsening status for subjects with UC.

The CDAI score and SES-CD will be jointly used to define moderately to severely active CD, ensuring that subjects with CD will have active symptoms of the corresponding severity as well as endoscopic evidence of active disease for eligibility. After randomization, the CDAI score will be used to determine Responder, Non-responder, and Disease Worsening status for subjects with CD.

This study is based upon real-world outpatient clinical practice, where central endoscopy does not play a role in initiation of therapy, and where clinical signs/symptoms (and labs as applicable) and a provider's assessment are adequate to assess therapeutic response or non-response. This approach has been endorsed by the Toronto Consensus in 2015 {[Bressler 2015](#)}. Safety and tolerability will be assessed by the evaluation of adverse events (AEs), selected clinical laboratory parameters, vital signs, physical examinations, and ECGs all of which are standard safety evaluations in clinical development. All subjects who experience a $\geq 50\%$ decrease in sperm concentration and/or total motility and/or morphology will be followed for one or more spermatogenesis cycles, up to 1 year as needed, to assess for sperm parameter reversibility.

1.3.2. Rationale for the Choice of Dose and Dosing Interval

The 200 mg once daily dose level of filgotinib is currently the highest clinical dose being evaluated in Phase 3 studies of RA, UC, and CD. In Phase 2 trials in RA, pooled data with an exposure-response analysis demonstrated a dose-dependent increase in efficacy up to 200 mg total daily dose. In the Phase 2 study of CD, subjects treated in the 200 mg arm showed favorable response and remission rates (47% remission over 23% placebo and 59% response over 41% placebo). These results are consistent with the relationship observed between filgotinib exposures and inhibition of pSTAT1 activation (ex-vivo) following single and multiple filgotinib doses, where maximal inhibition of pSTAT1 activation (~78%) was achieved at or above 200 mg total daily dose and intermediate inhibition (~47%) at 100 mg {[Namour 2015](#)}. pSTAT1 data, in conjunction with considerations around the margin for nonclinical testicular findings, suggests assessing doses above 200 mg is not indicated.

1.4. Risk/Benefit Assessment for the Study

Inflammatory bowel diseases are progressive and potentially life-threatening disorders with few treatment options, many of which result in primary or secondary nonresponse. Inflammatory bowel disease may lead to increased risk of gastrointestinal malignancies, impairment in quality of life, and ultimate need for life-altering surgery. Current treatment options are limited in their ability to establish mucosal healing and clinical remission and have significant safety and efficacy limitations; for example, biologics have significant immunogenic risks, and steroids are associated with increased morbidity and mortality. Remission rates are generally low when compared to placebo rates across most therapies for IBD. There remains substantial unmet need

in IBD, particularly in moderate to severe disease. The lifelong nature of IBD increases the probability that subjects have cycled through various therapies, leaving few approved options.

Nonclinical studies in rats and dogs identified lymphoid tissues and testes as target organs for filgotinib in long-term repeat-dose toxicity studies. Although decreased lymphocyte numbers observed in nonclinical studies have not been seen in clinical studies, hematological assessment will be performed throughout the present study to ensure this potential risk is appropriately monitored. In both rats and dogs, microscopic findings in the testes included germ cell depletion and degeneration, with reduced sperm content and increased cell debris in the epididymis and reduction in fertility in male rats. The dog was determined to be the most sensitive species. When using the AUC at the NOAELs for dogs in the 26-week and 39-week chronic toxicity studies, and the 39-week targeted exposure toxicity study, the exposure margins compared with the highest proposed clinical dose of 200 mg once daily are 2.5, 1.9, and 3.6-fold respectively, in subjects with CD. To assess this potential risk to male fertility, the male safety clinical study described herein is planned to examine the effect of filgotinib (if any) on sperm/ejaculate parameters. Male subjects who enroll will be appropriately consented via the ICF wherein risk language is highlighted. Impaired spermatogenesis is considered to be a potential risk for filgotinib. Refer to the IB for further information about nonclinical and clinical testicular findings.

Filgotinib has shown an increased risk in embryofetal malformations in rats and rabbits at exposures similar to, or slightly higher than, exposures associated with a 200 mg once daily dose in CD subjects. As a result, highly effective contraception and male condoms will be required for male subjects with female partners of child bearing potential, which is expected to mitigate this risk.

JAK inhibition is expected to increase the risk of infection based on mechanism of action. Across the global studies in filgotinib, in general, active treatment arms have increased incidences of infection versus placebo. In the present protocol, treatment interruption and discontinuation considerations surrounding infections are incorporated, and sites and investigators will be trained regarding such circumstances. All subjects will be screened for tuberculosis (TB), and subjects with active or untreated latent infections will be excluded. Malignancy has been reported in subjects on filgotinib; in the present trial, subjects will be required to have up to date colorectal cancer surveillance in accordance with local guidelines, and subjects with recent malignancies will be excluded as outlined in the inclusion criteria. For further details about infections and malignancies, please reference the IB.

The potential benefits of JAK inhibition include improvement in clinical symptoms and mucosal and endoscopic healing. JAK inhibition may be efficacious in the treatment of IBD based on results from the Phase 2 study (FITZROY) of subjects with CD. In FITZROY, an increase in mean hemoglobin concentration was observed, without difference between filgotinib and placebo. No clinically significant changes from baseline in mean neutrophil counts or liver function tests were observed at 10 weeks. Filgotinib treated subjects showed an increase in high density lipoproteins (HDL) and no significant change in low density lipoproteins (LDL). Lipid and hemoglobin effects represent potential benefits in this population.

Overall clinical findings and laboratory changes reported with filgotinib are consistent with JAK 1 inhibition. Based on Phase 2 data the expected benefit of using filgotinib as proposed in this study is considered to outweigh any associated risks. In addition, the subject population in the present study will consent to a risk of potentially permanent infertility, thus individual male subjects in conjunction with the treating physician may evaluate the benefit-risk profile of filgotinib. A lack of response contingency from Week 13 onward in the current study, targeting Non-responders at Week 13 and any subject who experiences Disease Worsening thereafter, will enable early access to active drug or standard of care treatment when clinically indicated. This rescue approach, the provision of best supportive care, and the limited study duration, makes the use of placebo ethically acceptable for the specified duration.

An external multidisciplinary DMC, including an expert in male fertility, will be appointed to monitor the study.

The DMC has monitored the study until the date of protocol amendment 6, including the data for the second unblinded interim analysis (IA2). As of amendment 6, the DMC will be decommissioned. Details on the DMC's role have been described in a specific charter. The DMC's role will be transferred to the internal Sponsor Safety Management Team (SSMT). The SSMT is not involved in the conduct of the study and will evaluate safety data throughout the remainder of the study as part of continuous safety oversight across the filgotinib program.

Taking all of these considerations into account with respect to the filgotinib program, the early signals for efficacy demonstrated in a Phase 2 clinical trial in CD, as well as the beneficial findings in nonclinical models of disease and the overall safety, tolerability, and PK characteristics of filgotinib elucidated to date, there is a favorable benefit-risk profile for this agent in continued development as a treatment for UC and CD. The overall benefit-risk balance of this study is considered favorable.

For additional information about the risks of filgotinib, reference the latest version of the filgotinib IB.

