Appendix 4. CTCAE Grading Scale for Severity of Adverse Events

Please refer to the Common Terminology Criteria for Adverse Events (CTCAE) Version 4.03, which can be found at:

https://evs.nci.nih.gov/ftp1/CTCAE/CTCAE_4.03/CTCAE_4.03_2010-06-14_QuickReference_8.5x11.pdf.

For AEs associated with laboratory abnormalities, the event should be graded on the basis of the clinical severity in the context of the underlying conditions; this may or may not be in agreement with the grading of the laboratory abnormality.

The only modification to the CTCAE criteria is the addition of a Grade 1 upper respiratory infection as follows:

CTCAE v4.0 Term	Grade 1	Grade 2	Grade 3	Grade 4	Grade 5	CTCAE v4.03 AE Term Definition
Upper respiratory infection	Mild symptoms; symptomatic relief (eg, cough suppressant, decongestant)	Moderate symptoms; oral intervention indicated (eg, antibiotic, antifungal, antiviral)	IV antibiotic, antifungal, or antiviral intervention indicated; radiologic, endoscopic, or operative intervention indicated	Life-threatening consequences; urgent intervention indicated	Death	A disorder characterized by an infectious process involving the upper respiratory tract (nose, paranasal sinuses, pharynx, larynx, or trachea).

Appendix 5. Pregnancy Precautions, Definition for Female of Childbearing Potential, and Contraceptive Requirements

The administration of filgotinib in embryo-fetal animal development studies resulted in decreased numbers of viable rat fetuses, increased resorptions, and visceral and skeletal malformations. Similar effects were noted in the rabbit. A safety margin relative to human exposure has not been identified. Pregnancy is contraindicated during use of filgotinib.

For participation in this study, men must agree to use condoms during the study and for 90 days after the last dose of study drug. Female sexual partners of childbearing potential, defined below, should also consider use of highly effective contraception as outlined below.

1) Definitions

a. Definition of Childbearing Potential (for female sexual partners of male subjects)

For the purposes of this study, a female-born partner is considered of childbearing potential following the initiation of puberty (Tanner stage 2) until becoming post-menopausal, unless permanently sterile or with medically documented ovarian failure.

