Women are considered to be in a postmenopausal state when they are ≥ 54 years of age with cessation of previously occurring menses for ≥ 12 months without an alternative cause.

Permanent sterilization includes hysterectomy, bilateral oophorectomy, or bilateral salpingectomy in a female subject of any age.

b. Definition of Male Fertility

For the purposes of this study, a male-born subject is considered fertile after the initiation of puberty unless permanently sterilized by bilateral orchidectomy or has medical documentation of permanent male infertility.

2) Contraception for Female Sexual Partners of Male Subjects

a. Study Drug Effects on Pregnancy and Hormonal Contraception

Filgotinib is contraindicated in pregnancy as there is a possibility of human teratogenicity/fetotoxicity in early pregnancy based on non-clinical data. Data from a drug-drug interaction study of filgotinib and hormonal contraceptives (GS-US-417-3916) have demonstrated co-administration with filgotinib did not alter the pharmacokinetics of representative hormonal contraceptives (levonorgestrel/ethinyl estradiol). For male subjects, male condom should be used; for their female partners of childbearing potential an accepted contraceptive method should also be considered. Details are outlined below.

Please refer to the latest version of the filgotinib IB for additional information.

b. Contraception for Female Sexual Partners of Childbearing Potential

Male subjects in this study with female sexual partners of childbearing potential must agree to use a condom. Male subjects must share the following information with female sexual partners regarding which contraceptive methods are recommended, starting at the time of Screening until 90 days following the last dose of study drug in the male subject.

Contraceptive Methods include:

Complete abstinence from sexual intercourse of reproductive potential with the male subject. Abstinence is an acceptable method of contraception only when it is in line with the female sexual partner and male subject's preferred and usual lifestyle.

OR

Consistent and correct use of 1 of the following methods of birth control listed below.

- Intrauterine device (IUD) with a failure rate of <1% per year
- Tubal sterilization
- Essure micro-insert system (provided confirmation of success 3 months after procedure)
- Hormonal methods (each method *must* be used with a condom in the male partner)
 - Oral contraceptives (either combined or progesterone only)

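### Protocol Section 1.4 says both partner contraception and male condoms are required and relies on both to mitigate embryofetal risk; Appendix 5 makes the condom mandatory but use of a partner method advisory.

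*Protocol*

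**What the plan says.** Protocol Section 1.4 (Risk/Benefit Assessment) reports malformations in rats and rabbits at exposures close to those of the study dose. It then states that "highly effective contraception and male condoms will be required for male subjects with female partners of child bearing potential" and expects this to mitigate the risk.

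Appendix 5 (Pregnancy Precautions and Contraceptive Requirements) sets out the rules:

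- **Introduction.** For participation, "men must agree to use condoms during the study and for 90 days after the last dose of study drug". On the other measure: "Female sexual partners of childbearing potential, defined below, should also consider use of highly effective contraception as outlined below".
- **Item 2a.** The male condom is to be used, and "for their female partners of childbearing potential an accepted contraceptive method should also be considered".
- **Item 2b.** "Male subjects in this study with female sexual partners of childbearing potential must agree to use a condom". The subject must also give his partner information "regarding which contraceptive methods are recommended, starting at the time of Screening until 90 days following the last dose of study drug". A list follows: abstinence, or "Consistent and correct use of 1 of the following methods of birth control listed below". Hormonal methods on that list must be accompanied by a condom.
- **Item 3.** Condoms are again mandatory for the subject until 90 days after the last dose, and partners are again asked to consider one of the listed methods.

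Inclusion criterion 10 (Section 4.2) requires subjects who have heterosexual intercourse to agree to the protocol's contraceptive method or methods. It points to Appendix 5 for what these are and names only the condom.

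**The concern.** The benefit-risk assessment names two safeguards as requirements and credits both with reducing the embryofetal risk. A site working from Appendix 5 has grounds to enforce only one of them. An ethics committee reading Section 1.4 and an investigator reading Appendix 5 would therefore come away with different understandings of the same safety provision.

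The mismatch deserves attention because Appendix 5 itself says of the animal findings that "A safety margin relative to human exposure has not been identified", and it treats pregnancy as contraindicated during use of the drug. The protocol's account of how the risk is contained should not differ between its sections.

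**Working it through.** No arithmetic applies beyond a count of statements. The check sets the passages side by side. All are current Amendment 6 text, and neither redaction nor an amendment log explains the difference.

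| Place in protocol | Condom | Use of a partner method |
|---|---|---|
| Section 1.4 | Required | Required (highly effective) |
| Appendix 5, introduction | Mandatory (*must*) | To be considered (highly effective) |
| Appendix 5, item 2a | *Should* | To be considered (accepted method) |
| Appendix 5, item 2b | Mandatory (*must*) | Described as recommended; only sharing the information is mandatory |
| Appendix 5, hormonal methods in the 2b list | Mandatory if such a method is used | No obligation to choose one |
| Appendix 5, item 3 | Mandatory (*must*) | To be considered |
| Inclusion criterion 10 | Named | Deferred to Appendix 5 |

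**Count within Appendix 5.**
- Condom: 3 unconditional *must* statements (introduction, 2b, item 3) plus 1 conditional one (hormonal methods), so 3 + 1 = 4. Item 2a adds a softer *should*.
- Partner method, use: 3 statements that it be considered (introduction, 2a, item 3) plus 1 calling the methods recommended (2b), so 3 + 1 = 4 advisory statements and 0 mandatory ones.
- Partner method, information: 1 mandatory duty on the subject to share it.

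Section 1.4 has 1 statement, which requires both measures. The two places agree on the condom and disagree on the partner method.

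**Could another passage remove the conflict?**
1. *The list in item 2b.* Read alone, its instruction on consistent and correct use of one method could pass for a requirement. The sentence introducing it makes it the content of what the subject must tell his partner about recommended methods.
2. *The* must *beside hormonal methods.* It obliges the man to add a condom. It does not oblige the partner to use a method.
3. *Criterion 10.* Its optional plural, and its naming of condoms as one inclusion, leave room for a second method. Its content comes from Appendix 5, where only the condom is obligatory.
4. *A tie-break.* Section 7.6 lets the more conservative criterion prevail, but that concerns toxicity management and study drug discontinuation. No such rule was found for contraception.

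**Who is affected.** Under the Definition of Terms, the second interim analysis (IA2) follows after all subjects have reached Week 26. Section 8.8 says the monitoring committee's oversight up to Amendment 6 included the data for that analysis. New entry under criterion 10 is therefore not the main issue. The long-term extension runs up to 195 weeks and the condom rule to 90 days after the last dose, so the conflict chiefly concerns subjects in those periods. Their number is not given.

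**The case against.** The strongest reply is that Appendix 5 is not silent on the partner side. It imposes a duty to inform, fixes the period (Screening to 90 days after the last dose), lists methods and names unacceptable ones. In the introduction and item 3, the advice to consider a method is addressed to partners, who are not trial participants, so advisory wording is unsurprising there. *Should* is also an unreliable marker in this appendix, since item 2a uses it for the condom, which is mandatory elsewhere. Sites are sent to Appendix 5 by criterion 10, and Section 1.4 is narrative.

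Much of this stands. It would be wrong to infer that the partner method is ignored. It does not remove the conflict, however: item 3 is addressed to the male subject and requires only the condom, and no statement in Appendix 5 requires use of a partner method. Section 1.4 is also the protocol's own benefit-risk assessment, and its favorable conclusion is said to take all of its considerations into account.

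The stakes are limited. Partners are not dosed, and Appendix 5 treats a relevant drug concentration in a partner as only a theoretical possibility. The condom rule, the bar on sperm donation and the reporting of partner pregnancies are not in question.

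**Conclusion.** The inconsistency is real and sits in a safety provision: the benefit-risk assessment states and relies on a requirement that the operative appendix does not impose. It should be corrected. Its effect on risk cannot be sized, because the documents give no figure for partner exposure, for partners' use of contraception or for the number of subjects still affected. Endpoints, sample size and analyses do not depend on it.

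The conclusion assumes that Appendix 5 is what sites follow, as criterion 10 directs. Two stronger readings are not supported. A reader might infer that subjects were misinformed or partners left unprotected; that depends on the consent form and on site practice, neither of which is in the documents. A reader might also infer that one of the two passages is the correct rule; the documents do not say which was intended, and this review takes no position.

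**What to change.** Reconcile Section 1.4, inclusion criterion 10 and Appendix 5 so that all three state the same contraception requirement in the same terms. That includes one term for the partner method, which is called highly effective in some places and accepted in another. The mitigation statement in Section 1.4 should agree with the reconciled requirement. Check the consent form, which was not available here, and align it if affected.

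The cost is wording in up to three places in the protocol, plus the consent form if needed. Data collection and analysis do not change.
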